Exercise training and in particular high-intensity interval training (HIIT) improves maximal oxygen uptake (VO₂max) among healthy individuals and those with pulmonary disease.^(7, 15) ^(16, 17) Fitness gains from HIIT may derive from changes in metabolic and protein expression contributing to muscle adaptation as well as cardiovascular adaptations including increased left ventricular compliance and right ventricular remodeling.^(2, 8, 18, 19) For example, in rats the shift to glycolytic metabolism which accompanies pathologic right ventricular remodeling in pulmonary hypertension is attenuated by HIIT,^(2, 3) and pulmonary vascular remodeling and right ventricular function improves after HIIT.^(2, 20) However, whether HIIT improves symptoms or functional capacity in deployment-related respiratory disease has not been investigated. Moreover, given uncertainties regarding mechanisms of deployment-related respiratory disease, recommendations on management of this syndrome in general are lacking.⁽²¹⁾ Therefore, the **primary objectives of this study are: 1) generate hypotheses regarding the role of cardiac and pulmonary vascular abnormalities in contributing to exercise intolerance and 2) generate pilot data regarding the safety, feasibility, and efficacy of HIIT in improving functional capacity and alleviating symptoms in deployment-related respiratory disease.** The results will inform a larger investigation of extrapulmonary mechanisms of symptoms and exercise interventions in deployment-related respiratory disease.

III. Research Methods

A. Outcome Measures:

Primary Outcomes:

- VO₂max
- Health-related quality of life (SF-36)

Secondary Outcomes:

- Gas exchange (oxygen consumption [VO₂], carbon dioxide production [VCO₂] and minute ventilation to generate calculations of oxygen pulse [VO₂/HR], ventilatory efficiency [VE/VCO₂], and dead space fraction [estimated dead space / tidal volume])
- TTE parameters of cardiac function (right ventricular pulmonary artery systolic pressure, mid-cavity diameter, tricuspid annular plane systolic excursion, right ventricular longitudinal strain, left ventricular ejection fraction, transmural peak inflow velocity of early rapid diastolic filling / early diastolic mitral annular velocity [E/e'])
- Peripheral venous blood untargeted metabolomics
- Borg rating of perceived exertion (RPE)
- Participation (attendance at supervised exercise sessions and diary of home sessions)

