Feasibility of exercise training program: A three-week familiarization / physiologic adaptation period has been built into the HIIT program to maximize the likelihood of participants being able to successfully perform the exercise training program. However, there is still the possibility of individuals being unable to complete the full intended training program due to injury or other reasons. Successful completion of HIIT sessions (including meeting target heart rate) will be assessed by the study team at least every 4 weeks. If an individual demonstrates >3 sessions over a 4-week period in which they fail to meet the exercise prescription, a study team member will discuss with the participant barriers to meeting the exercise prescription and help identify ways to address those barriers as appropriate. If an individual develops an injury which prevents them from completing the prescribed exercise program, they will be transitioned to a continuous exercise training regimen if possible (i.e. substituting "light exercise" training sessions for HIIT sessions) until able to resume HIIT, at which time they will begin HIIT with a repeat three-week familiarization / physiologic adaptation period. If they are unable to complete continuous exercise training, they will discontinue exercise training until able to resume. Completion rates of HIIT and continuous exercise training will be assessed as part of the analysis of the study (Aim 2).

E. Data Analysis Plan:

Specific Aim 1:

Hypothesis 1A: Pulmonary vascular remodeling resulting from prior airborne hazards exposures increases exertional pulmonary arterial pressure and right ventricular afterload, resulting in compromised right ventricular exertional performance with abnormal oxygen pulse, ventilatory inefficiency and increased dead space fraction on CPET and increased pulmonary artery systolic pressure during exertion (relative to healthy population norms).(4) Oxygen pulse, ventilatory efficiency, and dead space fraction will be analyzed using descriptive statistics. Results will be presented in reference to healthy population norms (ATS/ACCP guidelines).(6) Pulmonary artery systolic pressure will be analyzed using descriptive statistics. Results will be presented in reference to healthy population norms (American Society of Echocardiography guidelines).(5)

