Hypothesis 1B: Increased right ventricular afterload causes maladaptive right ventricular remodeling which is reflected by increased glycolytic metabolites (compared to a reference healthy population).(2, 3) Metabolomics partial least squares discriminant analysis and t-test or ANOVA will be performed. Exercise metabolomics data collected in a healthy population (COMIRB 21-4354) will be used as a reference.

Hypothesis 1C: Impaired right ventricular performance contributes to reduced maximum oxygen consumption (VO2max) relative to healthy population norms, dyspnea and impaired health-related quality of life. VO2max will be analyzed using descriptive statistics and presented in reference to healthy population norms (ATS/ACCP guidelines).(6) Dyspnea and health-related quality of life will be assessed by SF-36 with scores analyzed by descriptive statistics. Scores will be presented in

reference to disease population references.(34, 35) Linear mixed models will be used to assess the relationship between impaired right ventricular performance as measured by pulmonary artery systolic pressure and VO2max. Covariates including BMI, gender, age and type of deployment-related respiratory disease will be included.

Specific Aim 2:

Hypothesis 2A: *HIIT is safe and feasible among military personnel suffering from deployment-related respiratory disease, with $\geq 80\%$ participation in prescribed sessions.*(8) Attendance will be calculated as (number of supervised sessions attended + unsupervised sessions reported by exercise diary) / total number of supervised + unsupervised sessions. Feasibility will be based upon attendance of $>80\%$ of prescribed exercise sessions, with separate analyses for HIIT sessions, “light exercise” sessions, and combined sessions. Safety/acceptability will be based upon an absence of major adverse events attributable to the exercise training program and $<5\%$ minor adverse events (calculated as the number of adverse events divided by the total number of exercise sessions throughout the program) attributable to the exercise training program.

Hypothesis 2B: *Participants will spend approximately 4.5 hours/week engaged in this program and will report that participation was feasible.* Total hours spent in exercise program will be calculated based upon number of supervised sessions and reported unsupervised sessions. Qualitative assessment of feasibility will be collected via narrative report.

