Hypothesis 2C: *Staff will spend approximately 2 hours/participant in exercise supervision and coordination. Staff will report that level of supervision and time commitment was appropriate and feasible.* Staff time spent in exercise supervision will be calculated by [hours spent supervising exercise / number of individuals supervised simultaneously + hours spent scheduling and/or coordinating]. Staff's qualitative assessment of feasibility will be collected via narrative report.

Specific Aim 3:

Hypothesis 3A: *HIIT induces positive right ventricular and pulmonary vascular remodeling, improving right ventricular performance and exertional cardiac output, reflected by decreased glycolytic metabolites on peripheral venous metabolomics; improved exertional pulmonary artery systolic pressure on TTE; and improved oxygen pulse, ventilatory efficiency, and dead space fraction on CPET. Additionally, markers of left ventricular diastolic function on TTE will improve reflecting general positive training adaptations of HIIT.*(8) Metabolomics heat maps, partial least squares discriminant analysis, and t-test or ANOVA will be performed to compare pre- vs post-exercise training glycolytic metabolites. Pulmonary artery systolic pressure on TTE and oxygen pulse, ventilatory efficiency, and dead space fraction on CPET will be analyzed using descriptive statistics and compared pre- and post-exercise program by t-test. Resting left ventricular diastolic function (E/e') will be analyzed using descriptive statistics and compared pre- and post-exercise training by t-test.

Hypothesis 3B: *HIIT improves VO2max among patients with deployment-related respiratory disease.* VO2max will be analyzed using descriptive statistics and compared pre- and post-exercise training by t-test.

Hypothesis 3C: *HIIT improves dyspnea and health-related quality of life (SF-36).* SF-36 pre- and post-exercise training will be analyzed using descriptive statistics and compared pre- and post-exercise training by t-test.

Results will be analyzed according to an intention-to-treat protocol. A p-value of <0.05 will be used to establish statistical significance. Statistical analysis will be performed using SAS v 9.4 (SAS Institute Inc., Cary, NC, USA). For metabolomics data, the MetaboAnalyst 4.0 package will be used for analysis and XY graphs will be created using GraphPad Prism 8 (GraphPad Software Inc., La Jolla, CA, United States).

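### Hypothesis 1C takes pulmonary artery systolic pressure as right ventricular performance, while the listed RV function measures have no stated analysis

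*Combined protocol and SAP*

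**What the plan says.** All of the following is in the combined protocol and SAP.

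- **Hypothesis 1C (Data Analysis Plan, Specific Aim 1).** Linear mixed models will relate VO2max to "impaired right ventricular performance as measured by pulmonary artery systolic pressure", with BMI, gender, age and disease type as covariates.
- **Hypothesis 1A.** Pulmonary vascular remodeling "increases exertional pulmonary arterial pressure and right ventricular afterload, resulting in compromised right ventricular exertional performance". For echocardiography, the stated analysis is: "Pulmonary artery systolic pressure will be analyzed using descriptive statistics".
- **Hypothesis 1B.** "Increased right ventricular afterload causes maladaptive right ventricular remodeling".
- **Hypothesis 3A.** The claim is that "HIIT induces positive right ventricular and pulmonary vascular remodeling, improving right ventricular performance and exertional cardiac output". The planned analysis is: "Pulmonary artery systolic pressure on TTE and oxygen pulse, ventilatory efficiency, and dead space fraction on CPET will be analyzed using descriptive statistics", followed by a pre/post t-test. Glycolytic metabolites and resting E/e' are also compared before and after training.
- **Outcome Measures (III.A).** The secondary echocardiographic outcomes include "tricuspid annular plane systolic excursion, right ventricular longitudinal strain", listed separately from pressure, and also RV mid-cavity diameter.
- **Study Design (III.C).** Visits 1B and 2B, where echocardiography takes place, are optional.

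**The concern.** The reasoning in Aim 1 is a chain: vascular remodeling raises pressure and afterload, afterload impairs the right ventricle, and the impaired ventricle limits VO2max. If pressure stands in for RV performance, the middle link is never examined. A relation between pressure and VO2max could appear whether or not the ventricle is impaired, yet following 1C as written would report it as an RV-performance finding.

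Aim 1 exists to generate this kind of hypothesis, and the protocol says that its results will inform larger studies of mechanism. A mislabelled mechanism could be carried into the next trial although the protocol already lists measures that bear on it more directly.

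**Working it through.** **The plan's only power figure.** It concerns VO2max, not the RV question. With difference 2, SD 1.8 (taken as the SD of the change, which the plan does not state) and two-sided alpha 0.05 (assumed), the normal approximation gives n = (1.8 × (1.960 + 1.282) / 2)² = 8.5, so 9; 9 / 0.90 = 10. This matches the stated 10. (A two-sided paired t calculation gives 11, or 13 after dropout.) Nothing below depends on it.

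**1. Role of pressure.** In 1A, compromised RV performance results from pressure and afterload. In 1B, afterload causes RV remodeling. In 1C, pressure is the measure of RV performance. So 1C measures the proposed effect by its proposed cause.

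**2. Listed echocardiographic outcomes against stated analyses.**

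| Parameter (III.A) | Analysis named in the Data Analysis Plan |
|---|---|
| Pulmonary artery systolic pressure | 1A, 1C, 3A |
| E/e' | 3A, as left ventricular diastolic function |
| RV mid-cavity diameter | none |
| TAPSE | none |
| RV longitudinal strain | none |
| Left ventricular ejection fraction | none |

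Two of six parameters have an analysis. The three RV function and size measures have none.

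**3. Direction of the pressure scale.** 3A expects both higher exertional cardiac output and improved pressure. Stress imaging at both visits targets 90–95% of peak heart rate from the baseline CPET. If stroke volume rises with training, flow at that heart rate rises; with vascular resistance unchanged, pressure would tend to rise too. A better-performing ventricle could then show a worse pressure. Pressure alone does not rank RV function.

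**4. The other 3A markers.** The Background (II) attributes HIIT gains to muscle adaptation and left ventricular compliance as well as RV remodeling. Oxygen pulse, ventilatory efficiency, dead space and metabolites are indirect and cannot isolate the RV part.

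Oxygen pulse at peak shows why. It is VO2/HR, so with peak heart rate unchanged its percentage change equals that of absolute VO2max. For the 2 ml/kg/min gain in the sample size section, at stable weight, on assumed baselines of 30 and 20 ml/kg/min (not in the documents): 2/30 = 6.7% and 2/20 = 10%. Oxygen pulse would rise by that much whatever the source of the VO2max gain. This illustrates an identity; it does not measure the defect.

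**5. Precision of the 1C model.** Assume one baseline record per participant and three disease types. Parameters: intercept, pressure, BMI, gender, age and type (2) = 7. Residual df = n − 7. The smallest partial correlation reaching two-sided p < 0.05 is r = t / √(t² + df):

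| n with echocardiography | df | t | r |
|---|---|---|---|
| 12 | 5 | 2.571 | 0.754 |
| 10 | 3 | 3.182 | 0.878 |
| 8 | 1 | 12.706 | 0.997 |

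Putting TAPSE or strain in place of pressure leaves these limits unchanged. The change corrects what is measured, not how precisely.

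**The case against.** The strongest reply has five parts.

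- **This is a hypothesis-generating pilot.** The protocol concedes that the lack of a control group limits efficacy conclusions. This stands, and it limits the weight of the point.
- **Pressure is also used as a sign.** The sentence in 1A that makes pressure a cause also lists raised exertional pressure among the accompanying findings, and Aim 1 asks about pulmonary vascular as well as cardiac abnormality. The pressure model is therefore legitimate for Aim 1 and should stay. Using pressure as both cause and sign still does not make it a measure of RV function.
- **3A is broader than RV performance.** It also claims pulmonary vascular remodeling, on which pressure, ventilatory efficiency and dead space do bear. E/e' is introduced separately, as a general training adaptation. A reader might infer that 3A has no support at all, or that a rise in oxygen pulse alone would count as success. The documents support neither: the markers are listed jointly, nothing says that one is enough, and oxygen pulse is not restricted to peak.
- **Echocardiography is optional.** RV measures may exist for fewer than 12 people. This stands, but it limits pressure equally.
- **TAPSE and strain also depend on load.** This is true, and it is a reason to present them beside pressure rather than in its place.

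**Conclusion.** The point holds for 1C on the wording alone: a pressure–VO2max association cannot be reported as an RV-performance association, and the RV function and size measures listed as outcomes have no stated analysis. For 3A the conclusion is narrower: the named markers are indirect evidence and cannot isolate an RV effect.

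It would go too far to say that 1C and 3A can say nothing about the right heart. 1C can still inform on pressure and afterload, and 3A on the pulmonary vascular side.

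The size is qualitative: three listed RV measures without an analysis and one mislabelled model. The 6.7–10% oxygen-pulse figure rests on assumed baselines, unchanged peak heart rate and stable weight, and the conclusion does not need it. The VO2max and SF-36 comparisons are unaffected.

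**What to change.** - **1C:** relate TAPSE and RV longitudinal strain (rest and stress where obtained) to VO2max as the RV function variables. Keep the pressure model, labelled pressure/afterload.
- **3A:** add TAPSE, RV strain and RV mid-cavity diameter to the pre/post comparison. State that a change in peak oxygen pulse that parallels VO2max is not independent evidence of RV improvement.
- **Both:** label all RV inference exploratory, and report the number of participants with echocardiography at each visit.

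**Cost.** The measures are already listed outcomes from the same echocardiograms, so no new procedure is needed. The additions are two models and three pre/post comparisons (2 + 3 = 5), or up to 10 if each is done at both rest and stress, in at most 12 participants. With p < 0.05 and no multiplicity adjustment stated, these need the exploratory label. Precision does not improve.

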Specific Aim 2: Demonstrate safety and feasibility of high-intensity interval training (HIIT) in individuals with deployment-related respiratory disease. The same participants described in Aim 1 will complete up to 12 weeks of HIIT. HIIT will include 3 weekly supervised sessions (10 minutes warm-up followed by 4 x 4-minute intervals [4 minutes at 90-95% peak heart rate followed by 3 minutes at 60-75% peak heart rate] followed by 3 minutes cool-down).(7) Participants will also complete three home sessions/week of 40 minutes aerobic exercise at moderate intensity (Borg rate of perceived exertion 12-14. Hypothesis 2A: HIIT is safe and feasible among military personnel suffering from deployment-related respiratory disease, with $\geq 80\%$ participation in prescribed sessions.(8) Hypothesis 2B: Participants will spend approximately 4.5 hours/week engaged in this program and will report that participation was feasible. Hypothesis 2C: Staff will spend approximately 2 hours/participant in exercise supervision and coordination (calculated by [hours spent supervising exercise / number of individuals supervised simultaneously + hours spent scheduling and/or coordinating]. Staff will report that level of supervision and time commitment was appropriate and feasible.

Specific Aim 3: Generate pilot data regarding impact of HIIT on cardiopulmonary performance and its efficacy in improving functional capacity and symptoms in deployment-related respiratory disease. Questionnaire (SF-36), CPET, and peripheral venous metabolomics will be repeated after HIIT intervention. Resting and stress TTE may be performed. Hypothesis 3A: HIIT induces positive right ventricular and pulmonary vascular remodeling, improving right ventricular performance and exertional cardiac output, reflected by decreased glycolytic

metabolites on peripheral venous metabolomics; improved exertional pulmonary artery systolic pressure on TTE (if obtained); and improved oxygen pulse, ventilatory efficiency, and dead space fraction on CPET. Additionally, markers of left ventricular diastolic function on TTE (if obtained) will improve reflecting general positive training adaptations of HIIT.⁽⁸⁾ Hypothesis 3B: HIIT improves VO₂max among patients with deployment-related respiratory disease. Hypothesis 3C: HIIT improves dyspnea and health-related quality of life (SF-36).

II. Background and Significance:

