- Adverse events (recorded at supervised exercise sessions or reported from home sessions)
- Time commitment per participant (for participants, calculated as sum of hours exercising; for staff, calculated as [hours spent supervising exercise / number of individuals supervised simultaneously + hours spent scheduling and/or coordinating for that participant])
- Qualitative feasibility collected via narrative survey of participants and staff

B. Description of Population to be Enrolled:

Men and women ages 18-65 with deployment-related respiratory disease and symptoms of exertional dyspnea or exercise intolerance residing in the Veterans Integrated Service Network (VISN) 19 and receiving some or all of their care at VA medical facilities throughout the Eastern Colorado Health Care System (ECHCS) will be recruited. We will enroll up to 12 eligible veterans.

- **Inclusion Criteria:**

- Deployment of ≥ 30 days to Iraq, Afghanistan, Kuwait, Saudi Arabia, Bahrain, Qatar, United Arab Emirates, Kyrgyzstan, or Djibouti after September 2001(11)
- New onset of cough, shortness of breath, chest tightness/wheezing, dyspnea on exertion or exercise intolerance which started during or after deployment(11)
- Definite or probable distal lung disease (≥ 1 hyperinflation, emphysema, bronchiolitis, small airways inflammation, peribronchiolar fibrosis, or granulomatous pneumonitis on surgical lung biopsy; or ≥ 2 centrilobular nodularity, air trapping, mosaicism, or bronchial wall thickening on chest CT),(11) definite or probable deployment-related asthma (≥ 1 increase in post-bronchodilator forced expiratory volume in 1 second [FEV₁] $\geq 12\%$ and ≥ 200 cc, or methacholine challenge with PC₂₀ FEV₁ ≤ 16 mg/mL)(11) or unexplained dyspnea on exertion or exercise intolerance despite noninvasive testing including pulmonary function testing, methacholine challenge, transthoracic echocardiography, and/or chest computed tomography(9, 13)
- Current symptoms of dyspnea on exertion or exercise intolerance
- Residence <90 miles from RMR VA and ability / willingness to attend in-person HIIT sessions and research visits

- **Exclusion criteria:**

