Anticipated risks of HIIT training include fatigue, shortness of breath and leg discomfort, and participants will be counseled of these risks. Additionally, study team will closely monitor for adverse events through observation as well as participant report. Adverse events will include the following: minor – hypotension (BP < 90/60), lightheadedness, hypoxemia (SpO₂ <80% for >60 seconds),(24) chest pain, arrhythmia, or need to terminate exercise for another reason; major – major adverse cardiac event (stroke, myocardial infarction or cardiovascular death) or hospitalization. Exercise session will be terminated for any minor adverse event and PI and study safety monitor will be notified. Patient will be referred to Emergency Room if any member of the study team or the participant feel referral is indicated. Additionally, participant will be evaluated by PI prior to engaging in any future sessions. If further participation is felt to be of risk to the patient by either PI or the study’s safety monitor, then participation in study will be terminated. Major adverse events are not anticipated, but if any should occur patient will be transported immediately to the Emergency Room. HIIT has been studied in various populations including those with good health but sedentary lifestyle,(8) moderate to severe asthma,(17) and coronary artery disease,(25) and similar or identical HIIT regimens to that described in this protocol studies have demonstrated >80% compliance without attributable adverse events.(8, 25) Additionally, the study design includes an initial baseline assessment with symptom-limited CPET. If the initial CPET identifies safety concerns with completing the study exercise protocol, those concerns will be addressed prior to participant completing any further intervention. If unable to be addressed then the participant will be removed from the study. Therefore, the proposed protocol is anticipated to be safe for participants.

Home exercise: In addition to HIIT sessions described above, participants will perform three sessions / week of 40 minutes aerobic exercise at moderate intensity (Borg rate of perceived exertion 12-14). Home exercise will be prescribed to minimize the risk of confounding from

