Sample Size: Based on published data in patients with asthma,(17) who represent the most similar disease phenotype undergoing HIIT interventions reported in the current literature, a sample size of 10 is anticipated to provide 90% power to detect a difference in VO₂max of 2 ml/kg/min after HIIT, assuming a standard deviation of 1.8 ml/kg/min at an alpha = 0.05 and up to a 10% dropout rate. For the purpose of this pilot study, a sample size of 12 is anticipated to yield sufficient preliminary data regarding cardiac and pulmonary vascular abnormalities and safety, feasibility and efficacy of HIIT in the described patient population with the intent of future analysis in a larger study.

F. Summarize Knowledge to be Gained:

This study will generate hypotheses of pulmonary vascular and cardiovascular contributions to exercise intolerance after airborne hazards exposure, particularly among patients who currently remain undiagnosed with traditional evaluation. Additionally, it will demonstrate safety and feasibility of HIIT in this population and generate preliminary data regarding its efficacy in improving cardiopulmonary performance and symptoms of exercise intolerance. **The results will 1) inform larger investigations of extrapulmonary mechanisms of post-deployment dyspnea, particularly pulmonary vascular and cardiovascular abnormalities and 2) provide justification for a randomized controlled trial of different exercise modalities' efficacy in improving exertional dyspnea after airborne hazards exposure.**

G. Funding:

This study will be supported by the Department of Veterans Affairs Airborne Hazards and Burn Pits Center of Excellence (AHPCE) Pilot Project Program Award #FY2023-001 and a CTRC Microgrant. The contents do not represent the views of the AHPCE, U.S. Department of Veterans Affairs or the United States Government.

H. References:

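### Hypothesis 2A's two-part rule cannot show that HIIT is safe: with no major event in 12 participants, the exact 95% upper limit on per-participant risk is still 26.5% (two-sided) or 22.1% (one-sided)

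*Combined protocol and SAP*

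**What the plan says.** The lead sentence of Specific Aim 2 (section I) sets out to demonstrate safety and feasibility. Hypothesis 2A under that aim is that "HIIT is safe and feasible among military personnel suffering from deployment-related respiratory disease". The Data Analysis Plan for Hypothesis 2A gives a decision rule in two parts, both of which must hold:

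- Major events: "Safety/acceptability will be based upon an absence of major adverse events attributable to the exercise training program".
- Minor events: fewer than 5% attributable "minor adverse events (calculated as the number of adverse events divided by the total number of exercise sessions throughout the program").

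The HIIT intervention text in section III.D defines a major event as "major adverse cardiac event (stroke, myocardial infarction or cardiovascular death) or hospitalization". On numbers, section III.B says "We will enroll up to 12 eligible veterans". Section F states the expected conclusion: "it will demonstrate safety and feasibility of HIIT in this population".

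Other places promise less. The Background gives an objective to "generate pilot data regarding the safety, feasibility, and efficacy of HIIT", the opening of the Study Design section says much the same, and the Sample Size paragraph says "a sample size of 12 is anticipated to yield sufficient preliminary data regarding cardiac and pulmonary vascular abnormalities and safety, feasibility and efficacy of HIIT". No section gives a confidence interval, an acceptable event rate or a precision statement for the safety result.

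**The concern.** The rule turns an observed count of zero into a statement that the intervention is safe. In a sample this small, a count of zero is a likely result over a range of true risks that nobody would describe as shown to be safe, and the plan attaches no interval that would let a reader see this.

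This is more than loose pilot language. The sentence in section F that promises to demonstrate safety promises only preliminary data on efficacy, so on its face safety is to be the firmer conclusion. The limitations text (Potential Scientific Problems) restricts conclusions on efficacy, because there is no control group, and says nothing to restrict conclusions on safety. At stake is what the final report may claim: applied as written, the rule permits a finding of safety that the data cannot carry.

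**Working it through.** **The plan's own figure.** There is none for safety. The only sample-size calculation concerns VO₂max (difference 2, SD 1.8, alpha 0.05, 90% power, up to 10% dropout). It reproduces with a paired normal approximation: (1.8 × (1.960 + 1.282) / 2)² = 8.51, rounded up to 9, and 9 / 0.9 = 10. It has no bearing on the precision of the safety result.

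**Inputs.** n = 12 participants, a maximum (section III.B); zero attributable major events, the first part of the rule (Hypothesis 2A). As an assumption, n = 10 shows the effect of incomplete follow-up; the plan's 10% dropout applied to 12 leaves 10.8.

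**Upper limit when no event is seen.** The exact (Clopper-Pearson) 95% upper limit for 0 of n is 1 − 0.025^(1/n) two-sided and 1 − 0.05^(1/n) one-sided.

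| n | Two-sided | One-sided |
|---|---|---|
| 12 | 1 − 0.025^(1/12) = 26.5% | 1 − 0.05^(1/12) = 22.1% |
| 10 | 1 − 0.025^(1/10) = 30.8% | 1 − 0.05^(1/10) = 25.9% |

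**How often the major-event part is met.** If the true per-participant risk is p, the chance of no event in 12 is (1 − p)^12. The values of p are illustrative, since the documents set no acceptable risk.

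| p | (1 − p)^12 |
|---|---|
| 5% | 0.95^12 = 54% |
| 10% | 0.90^12 = 28% |
| 20% | 0.80^12 = 7% |

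The full rule also needs the minor-event condition, so these are upper bounds on the chance of passing it. The chance of no event exceeds one half only when p is below 1 − 0.5^(1/12) = 5.6%.

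**What the minor-event condition adds.** At the full schedule there are 6 sessions a week × 12 weeks × 12 participants = 864 sessions. Five percent of 864 is 43.2, so up to 43 attributable minor events would satisfy the condition. It can fail a study that has no major event, but it says nothing about how large the major-event risk could be.

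**Size needed to exclude a given risk with zero events.** Solving (1 − p)^n ≤ 0.05 (one-sided) or ≤ 0.025 (two-sided) gives 29 or 36 participants for p = 10%, and 59 or 72 for p = 5%.

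**The case against.** The strongest reply is that this is avowedly a pilot. The title, the Background, the Study Design section and the Sample Size paragraph all treat 12 participants as preliminary, with larger studies to follow. That stands, and it means the fault lies in the conclusion assigned to the data and the missing precision statement, not in running a 12-person pilot. It does not remove the conflicting wording in Specific Aim 2, Hypothesis 2A and section F.

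A second reply is that safety does not rest on the count alone. The protocol cites similar regimens without attributable adverse events, requires a baseline exercise test that can identify safety concerns, and has a safety monitor review the study after six participants and at the end. These support conducting the study; none of them enters the Hypothesis 2A rule or narrows its interval.

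A third is to count sessions rather than people: 0 of 864 gives a one-sided limit of 1 − 0.05^(1/864) = 0.35% per session. That assumes independent sessions. Sessions within a person are not independent, and the participant is the natural unit for stroke, infarction, cardiovascular death or hospitalization.

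A reader might also infer more than the documents support:

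- That safety would be declared on the absence of major events alone. The minor-event condition must hold as well.
- That the rule would usually be passed whatever the risk. At 10% the major-event part is met only 28% of the time; it is met more often than not only below about 5.6%, and the documents do not say whether risks of that size are acceptable.
- That the true risk is thought to be near 26%. That figure is only the limit of what zero events would fail to exclude.
- That the later trial would be monitored less closely as a result. Section F says the results will justify a randomized trial of efficacy; nothing links the safety finding to that trial's risk statement or monitoring.

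**Conclusion.** The concern holds as a mismatch between rule and conclusion. Meeting both parts of Hypothesis 2A would be consistent with safety but would not demonstrate it: with all 12 participants evaluable and no major event, per-participant risks up to 26.5% (two-sided 95%) or 22.1% (one-sided 95%) are not excluded, and with fewer evaluable the limits are higher. The conclusion is the same under either interval. The claim also contradicts the protocol's own pilot and preliminary-data wording.

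The limits assume that participants are independent with a common risk and that each is followed for the whole program. The pass probabilities rest on illustrative risks. Neither the design nor the two-part criterion as a signal for further work is called into question.

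**What to change.** 1. In the Data Analysis Plan for Hypothesis 2A, report the number of participants with an attributable major event out of all who started HIIT, with an exact 95% confidence interval, stating whether it is one- or two-sided.
2. If the count is zero, state the result as *no attributable major event observed; risks up to X% not excluded*, with X taken from that interval, in place of a verdict that HIIT is safe.
3. Reword Specific Aim 2 and section F to say that the study will *provide preliminary safety data*, in line with the Background, Study Design and Sample Size text.
4. Keep both parts of the existing criterion, described as a go/no-go signal for the next trial.

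This costs wording in three places and one interval. It needs no added participants, data or procedures and changes no clinical rule. The downside is a more modest stated conclusion.
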